7. APPENDICES

Appendix 1: Proforma

A. Identification

Case No. ()

Registration No -----

Name -----

Age -----

Sex Male Female

Body weight ----- kg Height ----- m² BMI (Kg / m²) -----

Address -----

Date of admission -----

Date of discharge -----

B. Operations

1. Date - ----- Time start - ----- Time end - -----

2. Operative time - () min

C. Intraoperative complications

Yes **No**

- | | | |
|--------------------------------|--------------------------|--------------------------|
| 1. Bile duct injury |  |  |
| 2. Bowel injury |  |  |
| 3. Vascular injury |  |  |
| 4. Injury to nearby structures |  |  |
| 5. Others |  |  |

D. Conversion to other procedure (Group A)

Yes **No**

[figure not shown]
Conversion to open

E. Conversion to other procedure (Group B)

[figure not shown]
Yes **No**

- | | | |
|-----------------------|--------------------------|--------------------------|
| 1. Conversion to CLC |  |  |
| 3. Conversion to open |  |  |

[figure not shown]
F. Postoperative pain assessment by VAS (Mild pain is 1- 4, moderate pain is 5 – 7 and severe pain is 8- 10)

[figure not shown]
1. 12 hr postoperative time Mild Moderate severe

2. 24 hr postoperative time Mild Moderate severe

3. 36 hr postoperative time Mild Moderate severe

4. 48 hr postoperative time Mild Moderate severe

G. Rescue analgesic requirement (Injection Tramadol)

	1 st Dose	2 nd Dose	3 rd Dose	4 th Dose	5 th Dose	6 th Dose	7 th Dose
Time							
Dose							

H. Postoperative complications

Yes

No

1. Wound infection

2. Prolonged ileus

3. Others

I. Duration of hospital stay - ----- days

[figure not shown]

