4.5 Sample size determination

Target population of this study is patients with symptomatic gall stones requiring laparoscopic cholecystectomy and it will be carried out in surgical wards of No. (1) Military Hospital (700 bedded). The minimal required sample size can be calculated as follow;

$$n = \frac{(Z_{1-\alpha/2} + Z_{1-\beta})^2 (\sigma_1^2 + \sigma_2^2)}{(\mu_1 - \mu_2)^2} \quad (\text{Lwanga S.K. \& Lemeshow S., 1993})$$

n= minimum required sample size

For 95% confidence level, $Z_{1-\alpha/2} = 1.96$ (for two sided)

For power 80%, $Z_{1-\beta} = 0.84$

$\mu_1 = 2.85$ (Analgesic need after CLC) (Sreenivas et al, 2016)

$\mu_2 = 2.31$ (Analgesic need after TPPOP LC) (Sreenivas et al, 2016)

$\sigma_1 = 0.79$

$\sigma_2 = 1.02$

n = 44

After adding 10% drop out

$n_1 = 49$

The minimum required sample size will be 49 in each group, 98 in total.

By receiving the hospital statistics, patients who was treated by laparoscopic cholecystectomy were about 150 patients a year in No.(1) Military Hospital (700 bedded) Pyin Oo Lwin. So the require sample size can be met within the study period.

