4.7.9 Postoperative period

Nasogastric tube will be removed after operation. Antibiotics will be given single dose. If gallbladder perforation with bile spillage is present, antibiotics will be given total three doses.

For postoperative pain control, regular analgesic with paracetamol suppository (750 mg for <50 kg and 1 G for \geq 50 kg body weight of the patient) will be given 6 hourly up to 72 hours. The patient will be assessed the pain score by using visual analogue scale (VAS) within 12 hour, 24 hour, 36 hour and 48 hour. Rescue analgesia will be added with injection of intravenous tramadol 1mg/kg if VAS was more than 4 and/or if the patient suffers breakthrough pain or if the patient complain of pain between the assessments. Total number and dose of rescue analgesia will be recorded in the proforma.

Patient will be discharged according to discharge criteria. The postoperative hospital stay will be calculated and recorded in proforma for each patient. During the hospital stay all cases will be observed daily by the researcher for early postoperative complications till the patients are discharged from the hospital. The complications which will be observed are wound infection, prolonged ileus, bile duct injury and bowel injury. Complications will be diagnosed clinically and confirmed by relevant investigations. These complications will be recorded in the proforma. All the complicated cases will be treated under the experienced consultant surgeon together with the researcher. After resuming oral intake, oral cefixime 200 mg twice a day will be given up to 5th postoperative day. Patient will be ordered to take oral paracetamol 500 mg if they feel pain after discharge.

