5. DUMMY TABLES

Table 1. Age distribution in both study groups

No.	Age (Years)	Group A CLC		Group B TPPOP LC	
		No.	%	No.	%
1	<30				
2	31-40				
3	41-50				
4	51-60				
5	>60				
	Total				

Table 2. Sex distribution in both study groups

No.	Sex	Group A CLC		Group B TPPOP LC	
		No.	%	No.	%
1	Male				
2	Female				
	Total				

Table 3. Comparison of operation time between both study groups

Operation time (minutes)	Group A CLC		Group B TPPOP LC		P value
	No.	%	No.	%	
30 – 60					
61 – 90					
91 – 120					
>120					
Total					
Mean \pm SD					

Table 4. Comparison of intraoperative complications in both study groups

Intraoperative complications	Group A CLC		Group B TPPOP LC		P value
	No.	%	No.	%	
Bile duct injury					
Bowel injury					
Vascular injury					
Injury to nearby structures					
Others					
Total					

Table 5. Rate of conversion to open cholecystectomy in group A (CLC)

Conversion to other procedure	Group A CLC		P value
	No.	%	
Conversion to open procedure			
Total			

Table 6. Rate of conversion to other procedures in group B (TPPOP LC)

Conversion to other procedure	Group B TPPOP LC	
	No.	%
Conversion to CLC		
Conversion to open procedure		
Total		

Table 7. Comparison of rate of conversion to open procedure in both study groups

Conversion to open procedure	Group A CLC		Group B TPPOP LC		P value
	No.	%	No.	%	
Conversion to open					
Total					

Table 8. Postoperative pain assessment by VAS at 12 hour after operation

Severity of pain	Group A CLC		Group B TPPOP LC		P value
	No.	%	No.	%	
Mild					
Moderate					
Severe					
Total					

Table 9. Postoperative pain assessment by VAS at 24 hour after operation

Severity of pain	Group A CLC		Group B TPPOP LC		P value
	No.	%	No.	%	
Mild					
Moderate					
Severe					
Total					

Table 10. Postoperative pain assessment by VAS at 36 hour after operation

Severity of pain	Group A CLC		Group B TPPOP LC		P value
	No.	%	No.	%	
Mild					
Moderate					
Severe					
Total					

Table 11. Postoperative pain assessment by VAS at 48 hour after operation

Severity of pain	Group A CLC		Group B TPPOP LC		P value
	No.	%	No.	%	
Mild					
Moderate					
Severe					
Total					

Table 12. Rescue analgesic injection Tramadol requirement in both study groups

	Doses of Injection Tramadol requirement		P value
	Group A CLC	Group B TPPOP LC	
12 hour			
12 – 24 hour			
24 – 36 hour			
36 – 48 hour			
Total			
Mean \pm SD			

Table 13. Comparison of postoperative complications in both study groups

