Appendix 4: Visual Analogue Scale (VAS)

The postoperative pain will be evaluated according to the VAS (Visual Analog Scale). The VAS consists of a 10 cm line, one end marks with 'no pain' and the other 'the worst imaginable pain'. The patient marks the point on the line to indicate the pain intensity, he or she suffers. The clinician then measures the line from 0 end & scored. Mild pain is 1- 4, moderate pain is 5 – 7 and severe pain is 8- 10 (Sodhi and Fernando 2002).

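### VAS pain is measured as a 0 to 10 score, but the visible form and tables keep only three classes with no place for 0, which costs the pain comparison power by an amount the protocol does not fix.

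*Protocol*

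**What the plan says.** Postoperative pain is part of the fourth objective in section 3.2. Section 4.7.9 has it assessed by VAS at 12, 24, 36 and 48 hours.

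- **Instrument (Appendix 4).** The patient marks a 10 cm line with no pain at one end. "The clinician then measures the line from 0 end & scored".
- **Variable list (section 4.9).** The range is a score from 0 to 10, but the scale of measurement is given as categorical.
- **Proforma, item F (Appendix 1).** At each of the four times the visible form offers mild, moderate or severe, with the key "Mild pain is 1- 4, moderate pain is 5 – 7 and severe pain is 8- 10". Appendix 4 repeats the same bands.
- **Dummy tables (section 5).** Table 8, "Postoperative pain assessment by VAS at 12 hour after operation", and Tables 9-11 have rows for mild, moderate, severe and total. They have no row for no pain and none for mean and SD.
- **Rescue rule (sections 4.7.9 and 4.8.12).** One of the triggers is the numeric score: "if VAS was more than 4".
- **Analysis (section 4.10).** Chi-square is given as an example of a method for categorical data. Student's t test is planned for continuous variables.

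**The concern.** The protocol obtains a number and then, as far as the visible form shows, keeps only a coarse class. Two things follow.

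First, the classes do not cover the scale. A pain-free patient has a valid score of 0 and no class to go in. Whoever fills in the form must tick mild or leave the item blank, and no rule says which. If the line is read in decimals, further readings fall between the bands.

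Second, three classes carry less information than the score. Reduced pain is one of the advantages that sections 1.2 and 1.3 put forward for fewer ports, so this is a comparison the trial should make efficiently. The form is the place to settle it: a later analysis plan can choose another test, but it cannot recover scores that were never written down.

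**Working it through.** **1. Classes against the scale**

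| VAS reading | Valid under 4.9 and Appendix 4? | Class in item F and Tables 8-11 |
|---|---|---|
| 0 | yes | none |
| between 0 and 1 | yes, if decimals are kept | none |
| 1 to 4 | yes | mild |
| between 4 and 5 | yes, if decimals are kept | none, though above 4 for the rescue rule |
| 5 to 7 | yes | moderate |
| between 7 and 8 | yes, if decimals are kept | none |
| 8 to 10 | yes | severe |

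Rounding to whole numbers would close the gaps at 4-5 and 7-8. It would not give 0 a class.

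**2. The protocol's own power figure**

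Section 4.5 uses a two-sided 5% level, 80% power, analgesic need of 2.85 against 2.31, and SDs of 0.79 and 1.02:

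n = (1.96 + 0.84)² × (0.79² + 1.02²) / (2.85 − 2.31)² = 7.84 × 1.6645 / 0.2916 = 44.75

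The protocol states 44, and 49 after 10% dropout (44/0.9 = 48.9). The figure reproduces to within rounding. It concerns analgesic need. The protocol gives no mean, SD, difference or power for VAS, so every VAS input below is an assumption.

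**3. Readings without a class, for illustration**

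Assume VAS is normal with mean 3 and SD 1.7.

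- Decimals kept: below 1, 12.0%; between 4 and 5, 15.8%; between 7 and 8, 0.8%. The total is about 29%.
- Rounded to whole numbers: only 0 is left out, meaning values below 0.5, or 7.1%.

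**4. Power at one time point**

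Normal VAS clipped to 0-10, 45 per arm (44.75 rounded up), 1-point difference, two-sided 5% level, 6,000 simulated trials per row. For the classes, scores are rounded to whole numbers and 0 is counted as mild, so every patient is classified. This isolates the cost of grouping from the cost of the gaps in step 3. Relative loss = 1 − (chi-square power / t test power).

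| Means, SD | t test on score | Three-class chi-square | Rank test on classes | Relative loss, chi-square |
|---|---|---|---|---|
| 2.5 vs 1.5, SD 1.5 | 87.0% | 30.5% | 26.9% | 65% |
| 3 vs 2, SD 1.7 | 77.8% | 38.8% | 40.7% | 50% |
| 4 vs 3, SD 2 | 64.8% | 33.7% | 43.9% | 48% |
| 5 vs 4, SD 1.7 | 79.0% | 52.2% | 64.3% | 34% |
| 6 vs 5, SD 1.7 | 78.3% | 55.8% | 66.2% | 29% |

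Repeat runs differ by one or two points, hence about 30-57% for chi-square over these rows. Two edge cases: 6 vs 5 with SD 1.5 gives 87.5% against 65.5% (25% loss), and 2 vs 1 with SD 1.5 gives 85.5% against 11.4% (87% loss). At low pain almost everyone is mild, and the classes can hardly differ.

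**5. A second set of assumptions**

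Borrow the standardised difference from section 4.5: 0.54 / √(1.6645/2) = 0.54 / 0.912 = 0.59. With 44 per arm and SD 1-2, the t test has power 0.75-0.79. Chi-square on three classes has 0.37-0.59 for control means 4-7 and 0.00-0.36 for control means 2-3.

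**The case against.** Several points on the other side have force.

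- **The size of the power loss is not in the document.** This stands. A reader might infer that about half the power is lost. That describes mean pain of about 3 to 4; other equally admissible assumptions give a quarter or nearly all.
- **Whole-number scoring may be intended.** The bands are written in whole numbers, and on that scale a score above 4 begins where moderate begins. The gaps at 4-5 and 7-8 therefore depend on an unstated reading rule, and so does most of the 29% in step 3. A reader might take that 29% together with the power figures, but the first keeps decimals and the second rounds. The gap at 0 remains either way.
- **Chi-square is only an example.** Section 4.10 leaves room for an ordinal test, and Tables 8-11 name no test. Ordering and repeated measurement may properly be left to an analysis plan, so they are not faulted here. An ordinal test recovers part of the loss in some scenarios and none at the lowest pain level in the main table.
- **A score box may exist on the original form.** Figures near item F are not shown, so a reader should not infer that the scores are certainly lost. But the visible form prints a numeric entry for operation time, hospital stay and tramadol doses and none for VAS. Tables 3, 12 and 14 carry mean and SD while Tables 8-11 do not. That pattern looks like a design choice.

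**Conclusion.** The point holds in a limited form. It is certain that the written classes have no place for a score of 0, and that section 4.9 describes a 0 to 10 score while labelling it categorical. It is very likely, from the visible form and tables, that only the class is kept and analysed. Whether readings between the bands are also left out depends on a rounding rule that the protocol does not give. The bands and the rescue wording need to be reconciled on this.

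Grouping weakens the pain comparison by an amount the protocol does not allow to be fixed. In the five assumed scenarios, power drops from about 65-87% to about 30-57%, a relative loss of roughly a quarter to two thirds, with more at lower pain levels. These figures assume roughly normal scores, a 1-point difference, 45 per arm and one time point.

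A reader might also infer that the trial's 80% power is compromised. The documents do not support that: the sample size rests on analgesic need, for which the proforma records each dose and its time and Table 12 reports mean and SD.

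**What to change.** - Add a numeric VAS field, in cm or mm, to proforma item F at 12, 24, 36 and 48 hours.
- List VAS as numerical in section 4.9.
- Add mean (SD) per group and the mean difference with 95% CI to Tables 8-11, using the t test that section 4.10 already plans for continuous variables.
- If the classes are kept as a supplement, add one for no pain (score 0), make the bands contiguous and state how the line is read. Reconcile this with the wording of the rescue rule in sections 4.7.9 and 4.8.12.

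The cost is one form field at each of the four times and revised table shells. The measurement is already being taken, so there is no added burden on patients and no change to the sample size.

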Appendix 3: Flow Chart

Flow chart of study design

Appendix 4: Visual Analogue Scale (VAS)

The postoperative pain will be evaluated according to the VAS (Visual Analog Scale). The VAS consists of a 10 cm line, one end marks with 'no pain' and the other 'the worst imaginable pain'. The patient marks the point on the line to indicate the pain intensity, he or she suffers. The clinician then measures the line from 0 end & scored. Mild pain is 1- 4, moderate pain is 5 – 7 and severe pain is 8- 10 (Sodhi and Fernando 2002).

Appendix 5: Gantt Chart

	2019												2020												2021											
Month	1	2	3	4	5	6	7	8	9	10	11	12	1	2	3	4	5	6	7	8	9	10	11	12	1	2	3	4	5	6	7	8	9	10	11	12
Protocol Writing																																				
Data Collection																																				
Data Analysis																																				
Thesis Writing																																				
Defend Period
